## 9.0 STUDY MONITORING

Nu-Life will monitor the study according to good clinical practice. The Principal Investigator will work with a representative from Nu-Life to ensure the study is conducted according to this protocol and that all study matters are properly communicated.

# Appendix 3: Study Process Maps

## NU-V3 BASELINE VISIT PROCESS MAP

[figure not shown]

**NU-V3 WEEKLY VISIT PROCESS MAPS**

**Weeks 2-8**

**Weeks 9-12**

## Appendix 4: Eligibility Checklist

**NU-V3 Protocol No. 1**

### SCREENING AND ELIGIBILITY CHECKLIST

A Single-Arm, Phase I Study to Evaluate the Efficacy of the Nu-V3 Device for Patients with Pain, Anxiety, Depression, Sleeplessness

Subject Initials:
Subject Identification Number:
Date of Consent:

**STATEMENT OF ELIGIBILITY:**

This subject is  eligible /  ineligible for participation in the study.

Investigator Signature: \_\_\_\_\_ Date: \_\_\_\_\_

Printed Name: \_\_\_\_\_

**INCLUSION CRITERIA (all questions should be answered YES – If question is answered No, subject is not eligible for participation)**

Yes	No	
		Participant is at least 18 years of age
		Participant presents with one or more of the following symptoms: pain, anxiety, depression, and/or sleeplessness
		Participant is capable of understanding the use and maintenance of the device
		Participant is capable and agreeing to participate in the ongoing assessment
		Participant has signed the Informed Consent Form
		Participant can commit to follow all protocol study time-points

If any of the above boxes are checked "No", the subject does not meet eligibility criteria

**EXCLUSION CRITERIA (all questions should be answered No – If question is answered Yes, subject is not eligible for participation)**

Yes	No	
		Participants with a Pacemaker
		Participants with an irregular heart rate or a heart rate lower than 60 beats per minute (bradycardia)
		Have had a transplant within the last 2 years
		Have had a heart attack or cardiac bypass surgery within the last 12 months
		History of substance abuse, including prescription drugs, within the last 12 months
		Patients with complaints of dizziness or lightheadedness within the last 3 months
		Women who are pregnant
		Participants with Diabetic Retinopathy
		Current Ear infection
		SBP < 100 and/or DBP < 60
		History of uncontrolled bipolar disorder within the last 12 months
		History of uncontrolled seizures within the last 12 months
		History of aneurysms
		History of syncope within the last 12 months
		Participants who have had a TIA or stroke within the last 12 months
		Participants with health problems deemed at risk for the study by the Principal Investigator
		Participants with any changes to Pain/Anxiety/Depression/Sleeplessness medications within last 60 days (participants that do not meet this medication change washout period may be delayed until 60-day period is met)
		Participants that are currently under adjudication process for disability support, VA or other

If any of the above boxes are checked "Yes", the subject does not meet eligibility criteria

# Appendix 5: Instructions for Use

## Instructions for Use

**1**

**Prepare the Patient's Ear**

Clean the area where the device and pads will be placed with the alcohol prep pads. Allow to dry for 60 seconds.

**2**

**Place the Device**

Carefully place the device behind the ear as shown. Adjust placement and clip for comfort.

**3**

**Attach the Pad Assembly**

Connect the PADS™ assembly to the device by inserting the pin into the connection port of the device.

**4**

**Place the Pads**

Carefully place each pad in the locations as indicated on the placement guide above. Place each pad on the flattest part of each position. Tweezers (included) may be helpful in placing the pads.

**5**

**Place the Protective Covers**

Once each pad is in place, remove a protective cover from its backing and place directly over each pad.

**6**

**Use and Care Instructions**

Once the device and all pads have been placed, instruct the patient on the use and care of the device for the time he or she will be wearing it and be sure they have the instructions to take with them.

**Preparing the Device**

The Nu-V3 Device and Packaging

**Step 1:** Remove the device and PADS™ assembly from the packaging.

**Step 2:** Gently remove the PADS™ assembly from its pouch.

**Step 3:** Remove the protective cover from the device tray and activate the batteries by pulling off the yellow tabs.

**Step 4:** Be sure the LED is flashing. Assemble the top and bottom of the device.

**Note:** The device is equipped with a miniature LED light, which begins to flash shortly after the batteries are activated. This helps to ensure the device is operating as intended. The device is in active stimulation mode for 3 hours and off for 3 hours. The LED flashes once per second in active mode and once every 10 seconds in off mode.

**Items Supplied:**

- Nu-V3 Device with non-activated batteries
- PADS™ Assembly
- Alcohol Prep Pad
- Instruction for Use & Safety Instructions
- Ear Covers

**Nu-Life Products, Inc**

Manufacturing and Supply of Nu-7

**Important:** Before applying the device, read all use and safety instructions on the reverse side.

# Appendix 6: Use and Care Instructions (Patient)

**Nu-Life Products, Inc**  
Manufacturing and Supply of Nu-V3

Indianapolis, Indiana  
www.Nu-V3/Patient.info

## Use and Care Instructions

Consult instructions for use

For Single Use Only

### SAFETY INSTRUCTIONS

These safety instructions are an integral part of the Nu-V3 and the therapy provided by the device and as such, must be followed closely to ensure the proper use of the device and safety of the treatment. These instructions for use and safety instructions are to be read and observed in full by every user. Treatment Provider and patient are both responsible for educating themselves and following these instructions and the proper use of the device as described in these instructions. Non-observance of the warnings and safety instructions may lead to injuries, infections or serious harm to the user and others.

The exclusive PADS™ assembly is only intended for single use. The re-use of single-use products represents a possible risk for the patient or user. Never place the exclusive gel pads on any location other than the auricular (ear) area, especially the eyes. It is important that all used devices and PADS™ assemblies are not reused in any way and that the device and PADS™ assembly is removed by the treatment provider or returned to the treatment provider by the patient or user.

Use of the device in the immediate vicinity of short-wave, or RF devices can be a cause of interference and should be avoided. The serial number for the Nu-V3 device is located on the packing for each device. These serial numbers are kept on file with the manufacturer and should be kept by the treatment provider and filed with the patient's reports on a regular basis.

### Absolute Contraindications

- History of dizziness or lightheadedness within the last 30 days
- Current ear infection
- Heart rate lower than 60 beats per minute (bradycardia)
- SBP < 100 and/or DBP < 60
- Heart attack within the last 12 months
- Cardiac bypass surgery within the last 12 months
- History of uncontrolled seizures
- Aneurysms
- History of an organ transplant within the last 2 years
- Pregnancy
- Diabetic Retinopathy
- Uncontrolled Bipolar Disorder within last 12 months

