### 3.2 Exclusion Criteria

- Participants with a Pacemaker
- Participants with irregular heart rate or a heart rate lower than 60 beats per minute (bradycardia)
- Have had a transplant within the last 2 years
- Have had a heart attack or cardiac bypass surgery within the last 12 months
- History of substance abuse, including prescription drugs, within the last 12 months
- Patients with complaints of dizziness or lightheadedness within the last 3 months
- Women who are pregnant

- Participants with Diabetic Retinopathy
- Current Ear infection
- SBP < 100 and/or DBP < 60
- History of uncontrolled bipolar disorder within the last 12 months
- History of uncontrolled seizures within the last 12 months
- History of Aneurysms
- History of syncope within the last 12 months
- Participants that have had a TIA or stroke within the last 12 months
- Participants with health problems deemed at risk for the study by the Principal Investigator
- Participants with any changes to Pain/Anxiety/Depression/Sleeplessness medications within last 60 days (participants that do not meet this medication-change washout period may be delayed until 60-day period is met)
- Participants that are currently under adjudication process for disability support, VA or other

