## 4.0 STUDY PROTOCOL

The Nu-V3 Clinical Study is a prospective, single-arm, open-label, multi-center study using the Nu-V3 cranial nerve stimulation treatment device in patients with pain, anxiety, depression, and/or sleeplessness.

For this Phase I study, a total of 50-100 patients at multiple centers will be registered for study participation. Study participants are those who have signed the informed consent form, met the inclusion and exclusion criteria, and are enrolled in the study at one of multiple sites. Enrolled participants are stratified based on their pain, anxiety, depression, and/or sleeplessness symptom presentation at baseline and treated with the Nu-V3 device for 8 weeks, then observed for an additional 4 weeks. Interim analysis of reported data will be based on baseline stratifications and conducted at 4, 8, and 12 weeks during this time. Post study, participants will be given the chance to continue with an optional maintenance treatment with the Nu-V3 device per a 2-weeks on, 2-weeks off schedule, for an additional 12 weeks, with an 8-week observation.

Subjects enrolled onto the Nu-V3 Clinical Trial will undergo the following regimen:

- At the baseline visit, patients will be asked to complete study questionnaires (Appendix 11) regarding all of the following symptoms: pain, anxiety, depression, and/or sleeplessness, as well as their quality of life, active medications, medical history, and demographical information.
- At each subsequent visit, patients will be asked to complete study questionnaires regarding all the following symptoms: pain, anxiety, depression, and/or sleeplessness, as well as their activity level and quality of life.
- The sessions will begin with the Nu-V3 device being placed on the left ear and three small pads (non-invasive) being placed on the ear. Each Nu-V3 device

lasts for up to 14 days with a change in the pads approximately 7 days into the treatment.

- Each session takes approximately 15-20 minutes. The placement of the device takes approximately 5 minutes and the remaining time is spent verifying ePRO form completion, and evaluating the patient for all device effects.
- The Nu-V3 device is mobile and is worn externally on the left ear 24 hours a day during treatment, fitting comfortably behind the ear. An electrical signal is sent to the external ear through coated wire leads attached to the device and adhesive pads which attach to three sites on the ear.

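### Optional maintenance places new devices at Weeks 13, 17 and 21 with no visible scheduled or recorded re-check of the contraindications that can change, and section 4.2 leaves 'infection' undefined

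*Protocol*

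**What the plan says.** Appendix 6 of the protocol separates absolute from relative contraindications. The absolute list includes "Heart rate lower than 60 beats per minute (bradycardia", systolic pressure below 100 or diastolic below 60, "Current ear infection", "History of dizziness or lightheadedness within the last 30 days", and pregnancy. Section 3.2 carries matching exclusions, with a longer dizziness window at entry: "Patients with complaints of dizziness or lightheadedness within the last 3 months".

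The leaflet is binding on whoever applies the device. Appendix 6 states: "These instructions for use and safety instructions are to be read and observed in full by every user". Appendix 5 lists the "Instruction for Use & Safety Instructions" among the items supplied with the device and adds: "Before applying the device, read all use and safety instructions on the reverse side".

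Section 4.0 offers "optional maintenance treatment with the Nu-V3 device per a 2-weeks on, 2-weeks off schedule, for an additional 12 weeks". In section 4.1, the main table marks Inclusion and Exclusion at Week 1 only. The post-study table marks a new device at Weeks 13, 17 and 21. It has no row for eligibility, vital signs, pregnancy or contraindications, although footnote 1, repeated beneath it, still names the Inclusion/Exclusion form. An in-office assessment and a Treatment Form are marked at each of the three placements.

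Section 4.0 describes a session as placing the device, confirming that the questionnaires are done, and evaluating device effects. The visible part of the Treatment Form (Appendix 9) asks for the serial number and whether the left ear was used. Section 4.2 lists infection among the reasons for leaving the left ear and treats wear on the right ear as a minor deviation.

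**The concern.** Heart rate, blood pressure, ear infection, dizziness and pregnancy can all change in the three to five months after entry. A Week 1 answer cannot settle them at Week 13 or later. Heart rate and blood pressure matter most here, because staff cannot know them without measuring them. They are also not incidental limits for this device: section 1.1 gives access to the vagus nerve and rebalancing of the autonomic nervous system as the proposed mechanism.

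At entry the protocol did not rely on the leaflet alone. It used a signed checklist (Appendix 4). Nothing comparable is visible when stimulation restarts after a break. The SAP's Accountability text provides an exit for participants not eligible for treatment, but that route works only if someone checks.

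Section 4.2 raises a related risk. Staff who read infection there as including ear infection could continue stimulation on the other ear in a participant for whom the leaflet rules the device out.

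**Working it through.** The documents give no figure for this interval, so there is none to reproduce. The inputs are the visit weeks in the two section 4.1 tables and the stated window of 3 days either side of each weekly visit.

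**Timing.** Nominal day of Week k = 7 × (k − 1), with Week 1 as day 0. The dizziness window on day d runs from d − 30 to d.

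| New device | Nominal day | With ±3 days | Days since previous in-office assessment | 30-day dizziness window |
|---|---|---|---|---|
| Week 13 | 7 × 12 = 84 | 81–87 | 84 − 77 = 7 (Week 12) | days 54–84 |
| Week 17 | 7 × 16 = 112 | 109–115 | 112 − 91 = 21 (Week 14) | days 82–112 |
| Week 21 | 7 × 20 = 140 | 137–143 | 140 − 119 = 21 (Week 18) | days 110–140 |

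Day 0 lies outside all three windows, so the Week 1 dizziness answer says nothing about the period that the leaflet cares about. No questionnaire is marked in the device-free Weeks 15–16 and 19–20.

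**Share of placements.** Main study: Weeks 1, 3, 5 and 7, so 4. Maintenance: Weeks 13, 17 and 21, so 3. For a participant who takes maintenance, 3 / (4 + 3) = 43% of placements fall in this phase. Uptake is not given.

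**How each contraindication could come to light at a maintenance placement.**
- *Heart rate and blood pressure:* only by measurement. No row, form item or session description visible after Week 1 mentions either.
- *Dizziness:* the evaluation of device effects may bring it out, but no field is visible for it.
- *Ear infection:* the person placing the pads may notice it, but again no field is visible.
- *Pregnancy:* the visible question is on the Medical History Form (Appendix 8), and section 4.0 collects medical history at baseline.

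**Section 4.2 beside the exclusions.** Section 3.2 and Appendix 6 each bar a current ear infection, and neither limits the bar to the ear being treated. Section 4.2 names infection as a reason for moving to the right ear and does not ask that it clear first. If infection means an ear infection, the texts conflict. If it means a skin infection under a pad, they need not. The protocol does not say which.

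**The case against.** The strongest reply is that the prohibition already exists. The leaflet comes with the device, must be read before application, and makes provider and patient both responsible. A reader might infer that the plan allows devices to be placed on participants with absolute contraindications; it does not. What is missing is a scheduled, recorded check.

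There are other safeguards. An in-office assessment of unstated content falls at each placement and 7 or 21 days before it. The Medications Form is marked at Week 12 and, counting columns in the extracted table, at Weeks 17 and 21; it could reveal treatment for some new conditions. The SAP also allows exit by physician decision. These might catch some cases, but none visibly requires a pulse or a blood pressure reading.

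Part of the source cannot be seen: the process maps, the consent pages, the Medications Form and possibly more of the Treatment Form. A reader might extend the point to the new devices at Weeks 3, 5 and 7. The documents do not support that, because a process map headed Weeks 2–8 exists and is not shown. The listed maps end at Week 12, which leaves maintenance uncovered by them. That is only weak evidence that no check exists, since a fuller Treatment Form would carry over.

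A reader might also multiply placements by 14 days of wear and treat the total as a measure of harm. It would count exposure only, since the documents give no rate of new contraindications. Nor does section 4.2 waive the ear-infection contraindication; it is ambiguous.

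Finally, maintenance is optional, the effectiveness endpoints end by Week 12, the device was judged nonsignificant risk, and the primary safety endpoint is reported unanticipated problems. The plan never promised to demonstrate compliance with the leaflet. All of this limits the consequence, but participants still wear the device in this phase.

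**Conclusion.** The point holds in a limited form. In optional maintenance the visible plan neither schedules nor records a re-check of the changeable absolute contraindications before a new device is placed, at nominal days 84, 112 and 140 after the only scheduled eligibility check. The firmest part is heart rate and blood pressure, which have no required measurement and no visible field after Week 1. It concerns 3 of 7 placements for a participant who takes maintenance. Expected harm cannot be sized from the documents.

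The section 4.2 point is conditional: there is a conflict if infection there includes ear infection. The undefined word is itself worth correcting.

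Confidence is moderate. The conclusion assumes that the unseen pages and any unseen part of the Treatment Form contain no such check. If they do, the first part falls away and only section 4.2 remains. The results of the 8-week primary analysis are not in question.

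**What to change.** At each maintenance placement (Weeks 13, 17 and 21), have the Treatment Form record heart rate, blood pressure and yes/no answers to the leaflet's absolute contraindications that can newly arise: dizziness in the last 30 days, current ear infection, pregnancy, and any other listed event since entry. The Appendix 4 checklist already supplies most of the items. Withhold the device while a contraindication is present, and keep the participant on the questionnaires.

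Amend section 4.2 so that a current ear infection leads to withholding until it resolves, not to a change of ear. Define infection there, for example by separating ear infection from skin infection at a pad site.

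The cost is a few minutes at three existing visits, a longer form and some lost device time in maintenance. No visit is added, and the 8-week primary endpoint is already complete by then. A yes/no question would still miss an unrecognised pregnancy; whether to test is for the sponsor to decide.

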### Relative Contraindications

- The following should be discussed with the patient's physician before use.
- Patients with a pacemaker
- History of syncope within the last 12 months
- History of TIA or stroke within the last 12 months
- Need for obtaining an MRI during the time the device is in place

Because the gel pads are non-invasive and use a specialized electro-gel to transmit the stimulation signal from the device to the nerves, the patient may or may not feel a gentle pulsing. This pulsing may diminish or stop as the body gets used to the stimulation. This is normal and is not an indication that the device is not working. The device is water resistant but not waterproof. When showering, patient should use the clear ear covers supplied with the device to ensure that the device stays dry. Do not allow the device to come in direct contact with water. Direct contact with water may result in the malfunction of the device.

### TECHNOLOGY DATA

Appliance: Non-invasive, Pulsed Stimulation Device Type description: Nu-V3 Device Power supply: 3 X 1.4 V batteries (Type AC 10E)  
Output: (Load impedance range 1k-10kΩ) max. 3.8V, Impulse interval 500ms, Impulse width 5ms, (1Hz / 5 ms / bipolar), max duration of treatment 14 x 24 hours.  
Classification: Class II (FDA) Duty Type: approx. 3h duty / 5h at rest (periodic duty) Weight incl. battery: .20 oz. Dimensions: 1.25 in x .5 in.

Form 0110001

The Nu-V3 Device

For professional use only

### Remarks

The stimulation received from the Nu-V3 device is controlled by a state-of-the-art micro-chip that creates a square, plus-minus wave, and turns itself off and on automatically every three (3) hours. This allows for an alternating stimulation and rest period.

### About the Nu-V3 Device and Accessories:

- The Nu-V3 device is a miniature microchip controlled nerve stimulation therapy device.
- The Nu-V3 device kit also includes an assembly consisting of three wires with non-invasive, exclusive electro gel PADS™.
- The Nu-V3 device is placed on the ear as indicated in the illustrations in this document.
- The device transmits low-frequency electric pulses.

### Recommendations on Indications for Use:

**IMPORTANT:** These Indications for Use are to be considered as a part of a physician's recommendation. Acute pain and chronic pain, anxiety, depression and sleeplessness

### TSA Security Information:

If traveling, the patient may keep this safety information available for TSA, or other airport safety organizations, should they inquire about the safety features of Nu-V3.

## Appendix 7: IRB Unanticipated Problem Form

### Nu-V3 Unanticipated Problem Form

Nu-V3 Version 1.0 Version Date: 07/Nov/2017	 Initial Report: _____ dd / mmm / yyyy	 Follow-up No. _____ _____ dd / mmm / yyyy	 Follow-up No. _____ _____ dd / mmm / yyyy	
Investigator Name: _____		Site: _____		
DEMOGRAPHICS				
Gender	Date of Birth	Height	Weight	
 Female  Male	_____/_____/_____ dd / mmm / yyyy	_____  in  cm	_____  lbs  kg	
ADVERSE EVENT INFORMATION				
SAE Term ( diagnosis preferred over signs/symptoms ):				
Onset Date _____/_____/_____ dd / mmm / yyyy	Serious Criteria ( select all that apply )	CTCAE Grade	Outcome	
Stop Date _____/_____/_____ DD / MON / YYYY	 Requires/prolongs inpatient hospitalization a  Life-threatening  Persistent or significant disability/incapacity  Congenital Anomaly/Birth Defect  Important medical event  Death b	 Grade 1 - Mild  Grade 2 - Moderate  Grade 3 - Severe  Grade 4 - Life-threatening  Grade 5 - Fatal	 Ongoing  Resolved  Resolved w/ sequelae c  Fatal	
Hospitalization:		Date of Admission _____ dd / mmm / yyyy	Date of Discharge _____ dd / mmm / yyyy	
Death:				
Date of death _____ dd / mmm / yyyy		Was autopsy completed?  Yes  No If yes, please forward report.		
		Is death certificate available?  Yes  No If yes, please forward.		
Describe sequelae:				
STUDY DEVICE INFORMATION				
Study Device	Date of First Use	Date of Last Use before SAE Onset	Relationship to Device	Action taken with Device
Nu-V3  N/A  Serial# _____	_____/_____/_____ dd / mmm / yyyy	_____/_____/_____ dd / mmm / yyyy	 Related   Unrelated	 None  Dose Reduced  Interrupted  Discontinued
Possible Cause of SAE other than Study Device ( select all that apply ):				
 Concurrent condition  Concurrent medication  Other, specify: _____				
_____ Condition term		_____ Medication name		

Effective Date: 07NOV2017  
Page 1 of 2

Document Title: Nu-V3 Unanticipated Problem Form

Nu-V3 Version 1.0 Version Date: 07/Nov/2017		Site Name:		Subject #:		
Nu-V3 Treatment Modifications: If action taken = interrupted or discontinued, did event stop once device was stopped?  Yes  No  If action taken = interrupted, did event recur once device was restarted?  Yes  No						
RELEVANT LABORATORY/DIAGNOSTIC TESTS  None						
Test Name		Date <small>dd/mm/yy</small>	Results/Value	Unit	Normal Range	
RELEVANT CONCOMITANT MEDICATIONS  None						
Medication	Start Date <small>dd/mm/yy</small>	Stop Date or Ongoing <small>dd/mm/yy</small>	Dose & Unit	Frequency	Route	Indication
		or  Ongoing				
		or  Ongoing				
		or  Ongoing				
		or  Ongoing				
RELEVANT MEDICAL HISTORY  None						
Diagnosis		Start Date <small>dd/mm/yy</small>	Stop Date or Ongoing <small>dd/mm/yy</small>			
			or  Ongoing			
			or  Ongoing			
			or  Ongoing			
			or  Ongoing			
NARRATIVE SUMMARY Describe the event in detail from onset through resolution. Include rationale for causality and any interventions given.						
REPORTER INFORMATION						
Investigator Name:		Phone:		Email address:		
Reporter Name:		Phone:		Email address:		
INVESTIGATOR SIGNATURE VERIFIES THAT EVENT HAS BEEN REVIEWED AND INVESTIGATOR CONCURS WITH THIS REPORT. I, the undersigned investigator, attest that I have reviewed this SAE Report. NOTE: Sign and date.						
Signature:			Date:			
Signature:			Date:			
Signature:			Date:			

SAE report may be emailed to Nu-Life Solutions Executive Medical Team  
 Email: [[contact]](mailto:[contact])

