## **7.0 ADVERSE EVENT(S)**

Potential unanticipated problems require prompt reporting to the central IRB and study sponsor. These problems potentially place subjects or others at greater risk of physical or psychological harm than was previously recognized, and warrant consideration of substantive changes in the protocol or informed consent process or other action in order to protect the safety, welfare, or rights of participants. The central IRB must be notified within 5 calendar days of the event and the study sponsor within 24 hours. The completed IRB Unanticipated Problem Form (Appendix 7) must be received by the central IRB within 10 calendar days of the event to avoid a major deviation.

Unanticipated problems are defined as those problems which alter the risks to subjects or others. This includes any study suspensions or holds. This form will be used to report any problem that is unforeseen or involves risk. One form will be used per event or problem.

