## 8.0 STUDY ENDPOINT and DATA ANALYSIS

### 8.1 Primary Endpoints: Primary endpoints consisted of the following:

Safety: The primary safety endpoint is the occurrence of reported unanticipated problems involving risk to subjects or others (“UPIRTSOs”). These UPIRTSOs are defined as those problems which alter the risks to subjects or others. This includes any study suspensions or holds. The primary safety endpoint analyses will be based on a risk-benefit conclusion.

Effectiveness: The primary effectiveness endpoints are an overall change in median reported symptoms of pain, anxiety, depression, and/or sleeplessness via numeric rating scales at 8 weeks. This primary effectiveness is measured by median reported symptom changes in pain, anxiety, depression, and/or sleeplessness for respective stratified populations via the following validated tools: Pain - Pain Intensity and Interference (PEG\_Scale), Anxiety - Generalized Anxiety Disorder 7-item (GAD-7) scale, Depression - Patient Health Questionnaire (PHQ-9), Sleeplessness - PROMIS short form 4a, and overall improvement of quality of life (QOL) - Patient’s Global Impression of Change (PGIC).

The hypothesis-driven criterion of effectiveness is to show that there is a statistically significant reduction in the median reported pain, anxiety, depression, and/or sleeplessness levels of patients using the Nu-V3 device. The second criterion is intended to show that there is a statistically significant improvement in reported quality of life and perceived treatment benefit, secondary to overall reported symptom reductions of pain, anxiety, depression, and/or sleeplessness.

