- Participants with any changes to Pain/Anxiety/Depression/Sleeplessness medications within last 60 days (participants that do not meet this medication change washout period may be delayed until 60-day period is met)
- Participants that are currently under adjudication process for disability support, VA or other

Accountability: Patients were exited from the study upon completing the final protocol-required questionnaires. In some cases, patients prematurely exited or withdrew from the study for the following reasons, including but not limited to:

- Not eligible for treatment (including patients who may have signed informed consent and been enrolled).
- Patient experienced a SAE or UPIRTSO.
- Voluntary withdrawal- the patient voluntarily chose not to participate further in the study.

- Lost to follow-up (LTFU) – the patient was more than 10 days late to a study visit and three documented attempts to contact the patient were unsuccessful. A patient who missed a study visit but attended subsequent visit (if required) was no longer considered lost to follow-up. A missed visit was considered a protocol deviation and the deviation was documented and reported.
- Physician decision – in the physician’s opinion, it was not in the best interest of the patient to continue study participation.

The tables below summarize patients who exited the study early, as well as those who completed all study participation as per protocol.

Table 1: Study Exit Summary- Early Exit (<8 weeks)			
	Phase I	Phase II	Total Enrolled
Voluntary Withdrawal			
Lost to Follow-Up			
Physician’s Decision			
SAE / UPIRTSO			
Other			
Overall “exited” Patients			

Table 2: Study Exit Summary (≥ 8 weeks)			
	Phase I	Phase II	Total Enrolled
Completion of Study as Planned			
Voluntary Withdrawal			
Lost to Follow-Up			
Physician’s Decision			
SAE / UPIRTSO			
Other			
Overall “exited” Patients			

Insert Study Exit Analysis Here

Section 1.0: Participant Flow

ClinicalTrials.gov

A service of the National Institutes of Health

Edited: 19 August 2014

Participant Flow Data Preparation Checklist

Overview: A tabular summary of the participants' progression through each stage of a study by group. Use this checklist with the [Participant Flow Template](#)^Δ and [Results Data Element Definitions](#).

	Information to have available for Participant Flow	Term

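### The form that reports the primary safety endpoint is worded as an SAE report and records nothing that shows whether a problem meets the endpoint definition

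*Protocol*

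**What the plan says.** Protocol section 8.1 sets the endpoint: "The primary safety endpoint is the occurrence of reported unanticipated problems involving risk to subjects or others". It continues: "These UPIRTSOs are defined as those problems which alter the risks to subjects or others", and adds: "This includes any study suspensions or holds". The SAP repeats this under Primary Endpoints. Seriousness is not part of the definition.

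Protocol section 7.0 names the Appendix 7 form for reporting, with one form per event or problem. It sets the filing rule as: "This form will be used to report any problem that is unforeseen or involves risk".

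Appendix 7 carries the title of an unanticipated problem form, but its body is that of an SAE report. The event term is labelled as an SAE term. Device exposure is asked as "Date of Last Use before SAE Onset" and alternative causes as "Possible Cause of SAE other than Study Device". The attestation reads "I, the undersigned investigator, attest that I have reviewed this SAE Report", and the e-mail route at the foot also calls it an SAE report.

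SAP Section 5.0 (Results) takes every reported UPIRTSO, in all registered patients, into the primary safety analysis. Table 4.1 in SAP Section 4.0 tabulates UPIRTSOs only.

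**The concern.** An endpoint defined by one property (altered risk) is collected on a form built around another (seriousness). Two things are at stake.

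- **Reporting.** An investigator with an unforeseen but mild device problem is handed a form that calls the event an SAE throughout and must be signed as one. Some such reports may not be made.
- **Classification.** Someone has to decide which filed forms are endpoint events. If the form does not record the defining properties, that decision cannot be checked against the data, and it would have to be reconstructed from narratives after the study.

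**Working it through.** No arithmetic applies. The plan gives no expected rate, threshold or test for the safety endpoint, so there is no figure to reproduce. The check sets the filing rule, the definition and the form side by side.

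**Step 1. Filing rule against endpoint definition.** Section 7.0 asks for a form if a problem is unforeseen *or* carries risk. Section 8.1 counts unanticipated problems that *change* the risk.

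| Type of problem | Form due under 7.0? | Endpoint event under 8.1? |
|---|---|---|
| Unforeseen, changes risk | Yes | Yes |
| Unforeseen, does not change risk | Yes | No |
| Foreseen, carries a risk already recognised | Yes | No |
| Study suspension or hold | Not stated in the filing rule itself, but inside the definition | Yes |

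Two of the four rows produce a form without an endpoint event. A site that follows section 7.0 exactly will therefore send in a mixture, and a sorting step is needed.

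**Step 2. What the form offers for sorting.**

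| Property | Coded on Appendix 7? |
|---|---|
| Seriousness | Yes, six criteria, all that apply; no explicit not-serious box |
| Severity | Yes, CTCAE Grades 1 to 5 |
| Relationship to device | Yes, related or unrelated |
| Unforeseen | No |
| Risk altered | No |
| Person at risk: participant or someone else | No |
| Study suspension or hold | No |

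Every property the endpoint turns on falls in the bottom four rows. Two forms with identical ticks can be one endpoint event and one non-event. The narrative prompt asks for a description of the event, the causality rationale and interventions. It does not ask about expectedness or altered risk.

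**Step 3. Whether the SAP supplies the sorting rule.** It does not. It refers to reported UPIRTSOs without saying how a filed form becomes one. If every filed form counts, the result follows the section 7.0 filing rule and not the section 8.1 definition.

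**Step 4. Whether another source fills the gap.** The assessment tables in Protocol section 4.1 have no adverse-event row. The Treatment Form (Appendix 9) shows serial number and ear placement with a reason. The PTB-7 questionnaire (Appendix 11) asks about major discomfort but is not tied to the safety endpoint. This covers the readable text only: the process maps in Appendix 3 are figures not shown, and Appendix 10 is not in the supplied text.

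**The case against.** The case against is that this is a labelling matter. Much of it is right, and it limits what can be claimed.

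- A reader might infer that the UPIRTSO count turns into a count of SAEs. The documents do not support that. Section 7.0 does not restrict filing to serious events, and the form's title says what it is for.
- A reader might infer that a non-serious problem cannot be entered. It can. No serious criterion need be ticked, Grade 1 is offered, and there is a free narrative.
- A reader might infer that nothing on the form separates events afterwards. Relatedness, seriousness, grade and hospitalisation dates are recorded, so an unrelated hospitalisation can be identified.
- A reader might take the SAP's exit reason, "Patient experienced a SAE or UPIRTSO", as proof that the SAP treats the two as different events. That rests on a single conjunction. SAP Tables 1 and 2 and the participant flow template (Figure 1.3) put both in one row, and neither term is distinguished from the other.
- Section 8.1 bases the safety analysis on a risk-benefit conclusion, so there is no numerical threshold that a shifted count would cross.

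What this leaves standing is the gap in Step 2. The codes that exist are not those in the definition, and a site that ignores the SAE wording still has nowhere to record them.

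**Conclusion.** The point holds in a limited form. UPIRTSO status cannot be verified from the filed forms, although the primary safety endpoint is a count of UPIRTSOs. The SAE wording may also discourage reports of non-serious problems; this is a plausible effect, not one the documents demonstrate.

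The miscount could go either way. Filed problems that do not change risk could be counted. Non-serious unforeseen problems, problems affecting other people, and suspensions or holds could be missed. With no SAE or UPIRTSO rates in the documents, neither its size nor its net direction can be estimated.

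The conclusion assumes that no unseen form or process map supplies the missing classification. It is worth fixing before data collection because the change is small and the information could not be reliably reconstructed later.

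**What to change.** **Appendix 7**

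1. Replace SAE with *event/problem* throughout, including the attestation and the e-mail line.
2. Put *Serious? Yes / No* before the seriousness criteria.
3. Add two coded fields: *Unforeseen? Yes / No* and *Alters risk to: subject / others / neither*.
4. Add an entry for a study suspension or hold.

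**SAP**

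1. Define SAE and UPIRTSO.
2. State that Table 4.1 and the primary safety analysis count only forms that meet the coded UPIRTSO definition.
3. Tabulate SAEs on a separate line.
4. Align the form's number: SAP Section 4.0 calls it Appendix 3, while in the protocol it is Appendix 7.

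The cost is one form revision, a short SAP addition, and a few more boxes for the investigator on each form.
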